### Efficacy and Safety Variables

The efficacy and safety variables in this study will be the change from the baseline assessment to the end of follow-up assessment or end of treatment assessment for the variables listed below. The variables will be determined from: the measurement of body weight, the recording of TPN prescriptions, blood and urine analyses, radiology reports, GI exams, and possible liver biopsies.

- Parenteral Nutrient Requirements (determined from the TPN/PN prescription)
  - TPN/PN infusions (days/week)
  - TPN/PN fluid volume (cc/week)
  - TPN calories (kcal/week)
  - TPN protein (g/week)
  - TPN lipid (g/week)
  - Intravenous vitamins (type and # of infusions/week)
  - Intravenous trace elements (type and # of infusions/week)
  
- Assessment of Nutritional Status
  - Body Composition
  - Body Weight
  
  - Nutrient and Metabolic Profile (Blood analyses)
  - Vitamins- A, B12, C, D, E, folate
  - Minerals and trace elements - calcium, phosphorus, iron, selenium, zinc
  - Serum Proteins - total protein, albumin, globulin
  - Lipid profile - essential fatty acids levels
  - Citrulline, D-lactic acid
  - Serum Electrolytes – (sodium, potassium, chloride, bicarbonate, magnesium)
  
- Assessment of Hydration Status/ Renal Function (Blood analyses)
  - Blood urea nitrogen
  - Serum creatinine

- Assessment of Liver Function (Blood analyses)  
Total bilirubin, direct and indirect bilirubin, alkaline phosphatase, SGOT, SGPT, LDH.
- Assessment of Upper and Lower GI tract/Liver  
Upper and Lower endoscopy, mucosal biopsies and bacterial cultures  
Ultrasound of abdomen/Small bowel follow through, Barium enema  
Liver biopsy (based on clinical indication)

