## **Study Design**

This study will be a prospective, non-randomized, open-label study of Omegaven™ with a total enrollment of 100 patients, for provision of parenteral lipid calories. The study cohort, receiving the PN at 1g/kg/day, will be compared to historical controls at UNMC where parenteral lipid calories were provided exclusively through soybean-based formulations, as well as, assessing the study cohorts need for small bowel and liver transplantation.

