#### **2. Evaluation**

During this period, the Investigator will evaluate to confirm eligibility. All these procedures are performed at initial evaluation on all patients in the Intestinal Rehabilitation Program, regardless of entry into a study. In addition to a review of body systems, the baseline evaluations will include the recording of body weight and routine urine and blood laboratory analyses. These blood and urine analyses will determine vitamin, trace element, essential fatty acid levels, serum electrolytes, hydration status, kidney function and liver function. Patients will also have radiology and GI exams. It is possible the evaluation may include a liver biopsy. The patient's pre-study TPN prescription will also be recorded.

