#### **3. Treatment**

The Treatment Period will not begin until the patient undergoes a full initial evaluation. Informed consent will be obtained before treatment is initiated. After the initial evaluation is complete and inclusion criteria are found to be met, therapy with Omegaven™ will be initiated at the goal dose of 1 gram per kilogram per day, over 12-24 hours. Omegaven™ will be infused intravenously through either a central or peripheral catheter alone or in conjunction with parenteral nutrition. If additional fat calories are needed, they will be provided via the central route. The same standards of care provided to all patients receiving parenteral nutrition solution will be followed, with routine nutritional monitoring.

In the event that a patient is unable to achieve adequate calories parenterally and is unable to tolerate enteral feeds, it may be necessary to evaluate whether or not the patient should continue the study with Omegaven™ or resume therapy with the conventional fat

emulsions so that additional parenteral fat calories can be given. The clinical team will determine if the patient should be removed from the protocol, and the IRB and FDA will be notified.

Orders for Omegaven™ will contain the following data elements;

- Total daily dose to administered in mL
- The hourly infusion rate (total daily dose ÷ the number of hours to be infused)

Prior to the administration of each Omegaven™ dose, two nurses will check the dose dispensed against the physician's orders and verify that the infusion pump settings (hourly rate, volume to be infused) are correct before the infusion is started.

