### **Duration of Therapy**

Patients will remain on Omegaven™ until weaned from PN and may continue monotherapy with Omegaven™ as an additional source of calories after the dextrose/protein portion of PN is discontinued.

In the event that a patient is listed for a liver or liver/intestinal transplant and an organ becomes available, the participation in this protocol will not preclude them from receiving the transplant.

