### **Discontinuation of Therapy**

Patients will continue to be followed by the UNMC Intestinal Rehabilitation Program upon discontinuation of therapy with Omegaven™ until they are completely free of any rehabilitation needs and are tolerating a full diet by mouth.

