### **Discontinuation of Therapy –**

- In the event that a patient is unable to achieve adequate calories parenterally and is unable to tolerate enteral feeds, it may be necessary to evaluate whether or not the patient should continue the study with Omegaven™ as monotherapy or resume therapy with conventional fat emulsions so that additional parenteral fat calories can be given.
- Adverse Event (AE) – Any patient with anaphylactic or allergic reactions to Omegaven™ will not continue treatment and will be withdrawn from the protocol.
- Inter-current Illness – If a patient develops an illness during the course of the study that is not associated with the condition under study and that requires treatment inconsistent with the protocol requirements (such as an interruption of regular participation in the study), the patient may be discontinued from further participation in the study. A patient may also be discontinued from the study if he develops an inter-current illness or complication that in any way justifies his withdrawal from the study. However, if an inter-current illness develops which can be managed without significant interference with the requirements of the protocol, the patient need not be discontinued.
- The patient will complete treatment with Omegaven™ in this study when he/she is completely off PN, develops a contraindication for further use, or the patient/family requests to be removed from the study.

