## Statistical Analysis

Data from the two sets of patient population will be pooled and compared (i.e., current protocol patients prescribed Omegaven™ PN compared to historical controls where parenteral lipid calories were provided exclusively through soybean-based formulations). Potential for effect in different patient populations will be minimized by matching patients enrolled in the Omegaven™ protocol to historical controls. Frequency matching will be utilized given the difficulty of paired matching in this patient population. Specific matching criteria will include gender, age, etiology of short bowel syndrome, and severity of liver disease (parenteral nutrition- associated liver disease).

Continuous data will be expressed as mean +/- SEM. A two-way repeated measure ANOVA will be used to compare differences in the two groups with respect to changes between the Evaluation assessment and the subsequent analyses performed at Treatment and Treatment/Follow-up Assessments. Incidence of adverse events in each treatment arm will be compared using Fisher's exact test. Univariate and multivariate analysis will be used to identify baseline factors that may influence outcome. A P-value <0.05 will be considered statistically significant.

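### Secondary changes from baseline are read at undated, course-dependent times, and historical controls have no stated time zero or reading date

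*Combined protocol and SAP*

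**What the plan says.** All references are to the combined protocol and SAP.

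- **Reading time.** Efficacy and Safety Variables defines the variables as "the change from the baseline assessment to the end of follow-up assessment or end of treatment assessment for the variables listed below". No week or month is given, and nothing says which of the two dates applies.
- **End of treatment.** Under Patient Discontinuation, the Discontinuation of Therapy list says: "The patient will complete treatment with Omegaven™ in this study when he/she is completely off PN". The same sentence adds a contraindication and a request by the patient or family. That list also allows stops for inadequate calories, allergic reaction and intercurrent illness, and investigators may withdraw a patient at any time. Treatment/Follow-up Period and Duration of Therapy allow Omegaven alone to continue after the rest of PN has stopped.
- **Follow-up.** The earlier Discontinuation of Therapy section has the program follow patients after Omegaven "until they are completely free of any rehabilitation needs and are tolerating a full diet by mouth".
- **Transplant.** Duration of Therapy says that, if an organ becomes available for a listed patient, "the participation in this protocol will not preclude them from receiving the transplant". Transplant is not named as an end of treatment.
- **Comparator.** Under Study Design the cohort "will be compared to historical controls at UNMC where parenteral lipid calories were provided exclusively through soybean-based formulations". Statistical Analysis adds frequency matching on gender, age, cause of short bowel and severity of liver disease.
- **Test.** Statistical Analysis plans a two-way repeated-measures ANOVA comparing the groups on "changes between the Evaluation assessment and the subsequent analyses performed at Treatment and Treatment/Follow-up Assessments".

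**The concern.** A comparison of change from baseline is interpretable only if baseline and reading time mean the same thing in both groups. Here the reading time in treated patients follows from how they fare. A patient who completes treatment by weaning has a PN requirement near zero at that reading by construction. The exception is any lipid still given as Omegaven alone.

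Controls never start Omegaven, so neither the start nor the end of treatment has a meaning for them until the plan supplies one. If it does not, the dates are settled when old charts are read, possibly with outcomes in view.

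What is at stake is the secondary objective, improvement in clinical measures of liver disease. It is also the stated Hypothesis, which is framed as normalization of liver enzymes and bilirubin.

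**Working it through.** The plan gives no figure to reproduce. The check sets the sections side by side and then uses two hypothetical calculations to show the mechanism.

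**1. Is a common reading time fixed anywhere?** No. Chemistries are taken one or more times a week in the Treatment Period and once a week as an outpatient, with the content at the investigator's discretion. The Treatment/Follow-up Assessments list has no schedule. The ANOVA names periods, and a period can last a different time in each patient. No section says which of the routine values enter the analysis.

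**2. Is a baseline fixed for controls?** No. The 2. Evaluation section says: "All these procedures are performed at initial evaluation on all patients in the Intestinal Rehabilitation Program, regardless of entry into a study". The 3. Treatment section adds: "The Treatment Period will not begin until the patient undergoes a full initial evaluation". If controls were program patients, which is not stated, they had an initial evaluation. That is the date of entry to the program. It need not be the date on which a control had a direct bilirubin of 2 mg/dL or more, as Inclusion Criteria require of treated patients.

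**3. Would applying the same rule to both groups cure it?** Not fully. Suppose controls are read at their own end of PN. Weaned patients in both groups then score near zero on PN requirement, whether weaning took a short or a long time, so a real difference in speed would be hidden. Liver tests would be read after unequal durations.

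**4. Hypothetical: reading liver tests or weight at different times.** All inputs are assumed except the 100 treated patients. Assume 100 controls, no drug effect, and the same drift of s SD per month in both groups, with mean reading times g months apart. With a two-sided 5% z test:

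- standard error = √(2/100) = 0.1414 SD; u = s × g / 0.1414
- chance of a false positive = Φ(u − 1.96) + Φ(−u − 1.96)
- example, s = 0.10 and g = 3: u = 0.30/0.1414 = 2.12; Φ(0.16) + Φ(−4.08) = 0.56

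| Drift (SD/month) | g = 0 | g = 1 | g = 3 | g = 6 |
|---|---|---|---|---|
| 0.05 | 0.05 | 0.06 | 0.19 | 0.56 |
| 0.10 | 0.05 | 0.11 | 0.56 | 0.99 |
| 0.20 | 0.05 | 0.29 | 0.99 | 1.00 |

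**5. Hypothetical: proportion off PN.** Assume the same monthly hazards in both groups: a for coming off PN and b for any other treatment end. Treated patients off PN at end of treatment: p = a/(a + b). With a = 0.05 and b = 0.02, p = 0.05/0.07 = 71.4%.

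- Controls read at their own end of PN by the same rule: gap 0.
- Controls read at month 6, other ends preventing weaning: p × (1 − e^(−0.07×6)) = 71.4% × 0.343 = 24.5%; gap 46.9 points.
- Controls read at month 6, weaning continuing after other ends: 1 − e^(−0.05×6) = 25.9%; gap 45.5 points.

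Over a = 0.03, 0.05 or 0.10, b = 0.02 or 0.04, and both cases, the gap from a fixed-month control reading is 26 to 47 points at 6 months and 1.5 to 33 at 12 months. At 24 months it is −19.5 to +18. Every negative value comes from the case in which weaning continues after other ends, which cannot hold for a patient who has died.

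The useful result is the contrast: with no drug effect, the answer runs from zero to large according to a choice that the plan leaves open.

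**The case against.** The strongest reply is that Efficacy and Safety Variables describes variables, while the between-group rule is in Statistical Analysis. That rule is a repeated-measures analysis with a time factor, not a single end reading. This is right as a description, and the point should not be put as if one final value decided the comparison. It does not resolve the problem, because a time factor aligns groups only when its levels mean the same time in both. Regular blood work and matching do not resolve it either: the first makes alignment possible without specifying it, and the second concerns who is compared, not when.

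Stronger readings are tempting, and the documents do not support them:

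- **That the plan would produce a false difference of 26 to 47 points.** No section says controls are read at a fixed month. The hazards are assumed, and proportion off PN is not itself a listed variable. The false-positive rates likewise rest on assumed drift, time gaps and number of controls.
- **That follow-up by definition ends at recovery.** The text describes how long the program looks after patients. That it also fixes the end of follow-up assessment is an inference.
- **That PN requirement is zero for everyone at end of treatment.** Treatment can stop for several other reasons, and Omegaven alone may continue.
- **That the primary outcome is affected.** Need for small bowel transplantation is not one of these change-from-baseline variables.

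**Conclusion.** The concern holds for the secondary comparisons of liver tests, weight and PN requirement. The plan offers two reading dates without a rule, and end of treatment depends on the patient's course. The ANOVA levels carry no dates, and controls have no time zero or reading date. This is more than missing detail, because the stated rule itself ties the reading to the patient's course, and applying it equally to controls would still not give comparable durations.

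The size and direction of any bias are unknown. The calculations show only that reading time alone can create a difference; they do not estimate one for this trial. The adverse-event comparison is also outside this point. The plan should be changed on this, preferably before control values are extracted.

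**What to change.** Amend Efficacy and Safety Variables and Statistical Analysis as follows.

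1. **Time zero.** Treated: start of Omegaven. Controls: a date on soybean lipid when the clinical inclusion criteria are met and the patient is on PN, alive and untransplanted. Choose that date without regard to the later course.
2. **Reading times.** Make the ANOVA time levels common pre-set times from time zero, for example 3, 6 and 12 months. Apply them to routinely collected liver tests, weight and PN prescriptions.
3. **Patients who stop.** Keep weaned and discontinued patients in with their actual values at those times.
4. **Transplant.** Do not count post-transplant liver tests, or PN stopped because of a transplant, as response to treatment.

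The cost is protocol wording and chart review of controls. No new visits are needed, since program patients have blood work at least weekly at first. Some control values will be missing, and testing thins out once patients are stable and off PN. The expectation of at least 30 more days on PN must be judged from control records. Values after death or transplant will not be available for analysis, so show by group how many patients contribute at each time. The change does not cover endoscopy, body composition or clinically indicated biopsy.

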## BACKGROUND AND RATIONALE

Patients with intestinal failure are unable to support growth or maintain health without some provision of nutrition parenterally. The Intestinal Rehabilitation Program at the University of Nebraska Medical Center is a multidisciplinary team focused on achieving enteral nutritional independence through optimization of intestinal function and autologous reconstruction of the GI tract. The program functions, along with small bowel transplantation, as part of the comprehensive intestinal failure program at UNMC. Many of our patients have excellent bowel rehabilitation potential given sufficient time for reconstruction and intestinal adaptation, but are limited by concurrent progression of parenteral nutrition-associated liver disease (PNALD). The ability to slow or reverse PNALD may dramatically impact on our ability to treat intestinal failure.

Lipids are necessary in PN dependent patients due to their high caloric value and essential fatty acid content. In the United States, most patients dependent upon PN receive parenteral fat emulsions composed of soybean oils, which have been implicated in predisposing patients to PN-associated liver disease (PNALD). There is evidence in the scientific literature supporting use of lipid formulations comprised mainly of omega-3 fatty acids to halt or reverse the progression of PNALD (Gura, 2008; Diamond, 2009). It is believed that fish oil-based formulations such as Omegaven™ mediate reduction of liver injury through inhibition of de novo lipogenesis, reduction of arachidonic acid-derived inflammatory mediators, and improved clearance of lipids from the serum. Animal studies have shown that IV fat emulsions (IFE), such as fish oil that are high in eicosapentaenic and docosahexaenoic acid, educe impairment of bile flow which is seen in cholestasis caused by conventional fat emulsions (Alwayn, 2005; Van Aerde, 1999). By administering Omegaven™ in place of conventional soybean fat emulsions we hope to reverse or prevent the progression of PNALD, allowing sufficient time for intestinal rehabilitation and eventual cessation of parenteral nutrition.

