We propose to conduct a prospective evaluation of the use of Omegaven™ for the provision of parenteral lipid calories in concert with an active ongoing program of intestinal rehabilitation. Our main outcome of interest will be need for small bowel transplantation, with secondary outcomes including improvement in clinical measures associated with PNALD and need for liver transplantation. This study will be conducted in both pediatric and adult intestinal rehabilitation patients.

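### Body weight is analysed as an unstandardised change in a cohort of children and adults, so a child's weight gain cannot be told apart from growth faltering

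*Combined protocol and SAP*

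**What the plan says.** Background and Rationale defines the population: "This study will be conducted in both pediatric and adult intestinal rehabilitation patients". The inclusion and exclusion criteria set no age limits or age strata. The same section describes the underlying problem partly in terms of growth: "Patients with intestinal failure are unable to support growth or maintain health without some provision of nutrition parenterally".

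Efficacy and Safety Variables gives the form of the outcomes: "The efficacy and safety variables in this study will be the change from the baseline assessment to the end of follow-up assessment", or to the end of treatment. On sources it says "The variables will be determined from: the measurement of body weight"; the sentence goes on to name PN prescriptions, laboratory tests, radiology, GI examinations and possible liver biopsies. Body weight is one of several items under nutritional status. The others are "Body Composition", with no method given, and a panel of blood analyses. At baseline, "the baseline evaluations will include the recording of body weight and routine urine and blood laboratory analyses". Height, length, percentiles, z-scores and growth velocity appear nowhere.

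Statistical Analysis says "Continuous data will be expressed as mean +/- SEM" and "A two-way repeated measure ANOVA will be used to compare differences in the two groups with respect to changes between the Evaluation assessment" and the later assessments. No split between children and adults is stated. Historical controls are frequency-matched on gender, age, etiology and severity of liver disease; age bands are not given. Treatment lasts until the patient is weaned from PN, and the program follows patients beyond that (Treatment/Follow-up Period; Discontinuation of Therapy).

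**The concern.** An adult on adequate nutrition is expected to hold weight, whereas a child is expected to gain. An unstandardised change puts both on one scale and adds each child's expected growth to any effect of nutrition. A gain in a child then does not show whether growth kept pace with age.

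The question matters to this trial. The plan foresees patients who cannot reach adequate calories parenterally (Treatment; Omegaven™; Discontinuation of Therapy), and weight is the only defined anthropometric variable that could show the consequence. The blood panel does not measure growth, and body composition has no method. What is at stake is the interpretation of one listed efficacy and safety variable.

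**Working it through.** The documents give no figure on this point: no expected growth, no SD of weight change, no number of controls. The arithmetic below is illustration under stated assumptions.

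**1. When a faltering child still shows a gain.** Assume the reference median weight grows by a fraction g over follow-up, the reference SD is cv times the median, and a child moves from z = 0 to z = −d. Then

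relative raw change = (1 + g)(1 − cv·d) − 1,

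which is positive when g > 1/(1 − cv·d) − 1. For a loss of 1 SD (d = 1):

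| Assumed cv | Threshold for g | Change at g = 10% | Change at g = 25% | Change at g = 50% |
|---|---|---|---|---|
| 0.10 | 1/0.90 − 1 = 11.1% | −1.0% | +12.5% | +35.0% |
| 0.12 | 1/0.88 − 1 = 13.6% | −3.2% | +10.0% | +32.0% |
| 0.15 | 1/0.85 − 1 = 17.6% | −6.5% | +6.2% | +27.5% |

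Masking is strong when expected growth is large relative to the loss. It is absent at 10% growth.

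**2. How often this could happen.** Assume an expected gain G in kg, k = 1 or 1.5 kg per z-unit, and a z-change with mean −0.5 or −1 and SD 0.5. Then P(raw gain) = Φ[(G + k·mean)/(0.5k)].

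- G = 2 to 3 kg: the lowest value is Φ[(2 − 1.5)/0.75] = Φ(0.67) = 0.75 and the highest is Φ[(3 − 0.5)/0.5] = Φ(5) ≈ 1.00.
- G = 1 kg: from Φ[(1 − 1.5)/0.75] = 0.25 to Φ[(1 − 0.5)/0.5] = 0.84.
- G = 0.5 kg: from Φ[(0.5 − 1.5)/0.75] = 0.09 to Φ(0) = 0.50.

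The range runs from 9% to 100%, depending mainly on expected growth over follow-up. Eligibility requires only a further 30 days of expected PN, so short horizons are possible.

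**3. The pooled mean.** With a share p of children, pooled mean = p·(child mean) + (1 − p)·(adult mean). Suppose the expected child gain is 3 kg. Half children gaining the full 3 kg and half adults holding weight give 0.5 × 3 + 0.5 × 0 = +1.5 kg. A group consisting only of children gaining half the expected amount also gives +1.5 kg. The same mean describes maintained nutrition in one case and growth faltering in the other.

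**4. What age matching leaves.** Frequency matching balances age at entry, within unstated bands. It does not balance follow-up time. If expected gain is 2 to 3 kg a year, a six-month difference in follow-up between the groups gives 0.5 × 2 = 1 kg to 0.5 × 3 = 1.5 kg of difference in weight change with no difference in nutrition. A z-score refers each weight to age at that weighing and so removes this component.

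**The case against.** The strongest answer is that the planned test is a comparison between groups. With controls matched on age and gender, expected growth is roughly common to both, so slower growth on Omegaven would appear as a smaller gain than in controls. This stands in part: matching gives real protection, and it would be wrong to say that raw weight change can show nothing. The protection is incomplete because age bands and the controls' follow-up lengths are not stated. It also does nothing for the reading of change within a group. The general univariate and multivariate analysis of baseline factors does not name age and leaves the scale of the variable unchanged.

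A second answer is that weight is only one item. That is correct. Body composition and a blood panel are listed beside it; the primary objective is need for small bowel transplantation, the secondary objectives concern measures of liver disease, and the hypothesis is tested on hepatic enzymes and bilirubin. Inadequate calories in an individual patient are assessed by the clinical team, not through this mean.

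A reader might go further and infer that the plan would record a faltering child as a nutritional success. The documents do not support this: they contain no responder rule, no score for nutritional status and no ranking of patients. A reader might also infer a definite loss of power. That cannot be supported, because the plan gives no SD, no effect size and no number of controls.

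**Conclusion.** The point holds as a minor one. As written, body weight enters as an unstandardised change in a mixed-age cohort with open-ended follow-up, so expected growth and nutritional effect are mixed. In children the sign of the change is ambiguous, and a mean over children and adults is not interpretable.

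The size depends on assumptions that the documents cannot settle. A 1 SD loss of weight-for-age is hidden once expected growth exceeds about 11% to 18% (cv 0.10 to 0.15, child starting at the reference median). The problem therefore concerns young, fast-growing children or long follow-up, and fades with little expected growth. Neither the primary objective nor the stated hypothesis is affected.

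**What to change.** In Efficacy and Safety Variables and in Statistical Analysis:

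- For patients under 18, analyse change in weight-for-age z-score, computed from recorded weight, sex and age at each weighing. Name one growth reference and use it for both the Omegaven patients and the historical controls.
- For adults, analyse percent change from the Evaluation weight.
- Report the two strata separately and give no pooled mean weight change.

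The cost is a change of wording and a lookup against the reference. Weight is already recorded, and age and gender are already needed for matching. Weight-for-age needs no height or length, so it can be computed for historical controls wherever dated weights exist. No visit, procedure or treatment changes. The small downside is two smaller strata, each less precise, instead of one pooled estimate.

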### **Dosing Instructions and Schedule**

During the treatment period, patients will receive an approximate daily infusion of Omegaven™ at a dose of 1g/kg/day, to be infused over 12-24 hours.

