### **Monitoring and Possible Dose Reductions**

In addition to standard nutritional monitoring, essential fatty acids will be sent monthly and serum triglyceride levels will be sent weekly. If lipid intolerance develops, defined as serum triglyceride levels > 200 mg/dL, the following will be considered prior to reducing the dose:

- a) If the level was obtained while the patient was receiving a continuous 24- hour infusion of Omegaven™, the total dose will be infused over 20 hours, and a repeat serum triglyceride level obtained prior to resuming the infusion 4 hours later.
- b) Other sources of lipid intolerance will be considered and addressed (drugs, renal disease)

If the triglycerides continue to remain high despite the aforementioned interventions, a dosage reduction of 25% of the current dose will be considered.

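### PN requirements are analysed as absolute weekly changes across children and adults, so growth and body size enter the result, and lipid g/week largely follows the assigned dose

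*Combined protocol and SAP*

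**What the plan says.** The section Efficacy and Safety Variables states: "The efficacy and safety variables in this study will be the change from the baseline assessment to the end of follow-up assessment", or to the end-of-treatment assessment. The first group in that list is "Parenteral Nutrient Requirements (determined from the TPN/PN prescription". It holds infusion days per week, volume in cc/week, calories in kcal/week, protein in g/week, "TPN lipid (g/week", and counts of vitamin and trace-element infusions. Evaluation Assessments repeats the list, and Treatment/Follow-up Assessments refers back to it. Body weight is listed separately, under nutritional status.

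On the population, Background and Rationale says: "This study will be conducted in both pediatric and adult intestinal rehabilitation patients". The eligibility criteria set no age or weight limit.

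On the lipid dose, Dosing Instructions and Schedule gives Omegaven "at a dose of 1g/kg/day". The Treatment section says "therapy with Omegaven™ will be initiated at the goal dose of 1 gram per kilogram per day, over 12-24 hours" and allows for more fat: "If additional fat calories are needed, they will be provided via the central route". For persistently high triglycerides, "a dosage reduction of 25% of the current dose will be considered". Disruption of Therapy allows interruption. Duration of Therapy continues Omegaven until the patient is weaned from PN, and lets it go on alone after the dextrose and protein have stopped.

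Statistical Analysis compares changes between the Omegaven cohort and historical soybean-lipid controls by two-way repeated-measures ANOVA at P<0.05. Controls are frequency matched on gender, age, etiology and liver disease severity. Weight, baseline PN and lipid dose are not matching factors, and no weight covariate or age stratum is named.

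**The concern.** An absolute weekly amount mixes two things: how dependent the patient is on PN, and how big the patient is. In a mixed-age cohort this has three effects.

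- A growing child on a constant per-kg prescription shows a rising requirement although nothing has worsened. Better growth, which would be a good result, counts against treatment.
- Patients with large weekly totals contribute most of the variance, so a real proportional fall is harder to detect.
- If the age mix still differs after matching, the same proportional response gives different mean changes in the two groups.

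Lipid has a further problem. The variable is read from the prescription, and the treatment under study is itself a lipid prescription. The baseline is the pre-study prescription, so the switch to Omegaven falls inside the measured change. Matching on age cannot remove a change that the assigned treatment imposes. If TPN calories include lipid calories, which the list does not rule out, part of this carries into kcal/week.

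What is at stake is how the supporting evidence on PN dependence is read. Background and Rationale names eventual cessation of PN as an aim.

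**Working it through.** The plan gives no figure for these variables to reproduce: no SD, effect size, weights, age mix or control lipid dose. All weights, prior doses and age mixes below are assumptions. From the documents come the 1 g/kg/day goal dose, the 25% reduction and the enrollment of 100.

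**1. Size and growth.** Lipid (g/week) = 7 × dose (g/kg/day) × weight (kg). At 1 g/kg/day:

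- 5 kg: 7 × 1 × 5 = 35; 20 kg: 140; 70 kg: 490. The range is 490 / 35 = 14-fold at one dose.
- Growth from 4 to 8 kg: 28 to 56 g/week, or +100%, with the per-kg dose unchanged.

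**2. The switch.** Change = 7 × weight × (1 − prior dose), in g/week:

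| Assumed prior dose (g/kg/day) | 20 kg | 70 kg |
|---|---|---|
| 0.5 | +70 | +245 |
| 1 | 0 | 0 |
| 2 | −140 | −490 |
| 3 | −280 | −980 |

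The artefact can go either way or be nil. The documents do not say which, because prior and control lipid doses are absent.

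**3. Later departures from the goal dose.** A 25% reduction at 20 kg gives 140 × 0.75 = 105 g/week, so lipid intolerance reads as a lower requirement. A 20-kg patient off dextrose and protein but still on Omegaven alone at the goal dose stays at 140. A patient fully off PN and Omegaven is at 0, which is a real signal.

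**4. Variance, bias and power for calories.** An illustrative simulation used 4,000 runs, 100 patients per group (the number of controls is not stated), and a two-sided t-test at 0.05 on change in kcal/week and on proportional change. Children: weight uniform from 3 to 15 kg (mean 9), 80 kcal/kg/day. Adults: mean 65 kg, SD 12, 25 kcal/kg/day. The proportional reduction had SD 0.30. Growth was not modelled.

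- Variance: mean daily PN calories are 9 × 80 = 720 for a child and 65 × 25 = 1,625 for an adult. The same proportional scatter gives an average adult (1,625 / 720)² = 5.1 times the variance of an average child.
- No true difference (40% reduction in both groups): the false-positive rate in kcal/week was 0.05 with 80% children in both groups, 0.10 at 80% v 70%, and 0.26 at 80% v 60%. The proportional scale stayed near 0.05. By hand, a 10-point imbalance shifts the difference by 7 × 0.4 × 0.10 × (1,625 − 720) = 253 kcal/week; the simulation gave 246.
- True difference (50% v 35% reduction), equal age mix: power in kcal/week was 0.82, 0.75 and 0.78 with 100%, 80% and 50% children. On the proportional scale it was 0.94. Check: 0.15 / (0.30 × √(2/100)) = 3.54, and 3.54 − 1.96 = 1.58, which gives 0.94.

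**5. What the better scale must do.** Per-kg values remove growth but still differ by age under these inputs (80 v 25 kcal/kg/day), so they need separate pediatric and adult results. Proportion of baseline removes size differences between patients, but must be taken on the per-kg amount; otherwise the child in step 1 still shows +100%.

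**The case against.** The strongest reply has four parts.

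**The dose is not fixed.** It is a goal that can be reduced, interrupted, supplemented, or ended at weaning. A reader might infer that lipid g/week is simply 7 × weight and that its comparison is a foregone conclusion. The documents do not support that: a patient who comes off PN and Omegaven goes to zero, and with the control dose unstated nobody can say which way the comparison would lean. This part stands. Reductions for triglycerides and interruptions for access or fluid limits do not rescue the variable, however, because they change it for reasons other than need.

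**The design already limits size bias.** Analysis is on change, controls are frequency matched on age, and baseline factors will be examined in multivariate analysis. With equal age mix the simulated false-positive rate was 0.05, so body size does not automatically create a false difference. This also stands; the inflation to 0.10 and 0.26 needs an imbalance that matching is meant to prevent. What remains is the power loss, and growth, which cancels between groups only if both grow alike over similar follow-up. The plan sets no common end time.

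**The group contains size-free measures.** A reader might infer that the PN variables cannot show whether dependence fell. They can: infusion days per week, and the vitamin and trace-element infusion counts, do not scale with body size.

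**The list is joint and unlabelled.** It does not call lipid an efficacy outcome, and lipid may be meant as a record. That is so, but nothing exempts it from the ANOVA on changes.

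**Conclusion.** The point holds in a limited form. Four supporting variables are defined as change in absolute weekly units in a mixed-age cohort with no weight scaling. Growth can then pass for rising requirement, larger patients dominate the variance, and any age imbalance left after matching can bias the group comparison. Lipid g/week is mostly a record of weight and assigned dose until full weaning.

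The growth example (+100% from 4 to 8 kg) is exact arithmetic on illustrative weights. The power figures (0.75 to 0.82 against 0.94) and false-positive rates depend on the assumed weights, calorie densities, age mix and response SD, and show the kind of effect rather than its size in this trial. The direction and size of the lipid artefact cannot be determined from the documents.

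A reader might also infer a threat to the trial's main conclusion. The documents do not support that: the primary objective is need for small bowel transplantation, and the hypothesis is measured by hepatic enzymes and bilirubin. This is a cheap improvement.

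**What to change.** In Efficacy and Safety Variables, Evaluation Assessments and Treatment/Follow-up Assessments, and in the analysis described under Statistical Analysis:

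- Express PN volume, calories and protein per kg of current body weight per day, or as a proportion of the patient's own baseline per-kg value.
- Show pediatric and adult results separately.
- Report TPN lipid as treatment exposure, described by group and not tested as an outcome.
- Measure PN dependence by non-lipid PN calories together with infusion days per week.
- State which recorded weight is used at each assessment. Weight is listed at Evaluation, daily in the outpatient period and at follow-up, but is not named in the in-hospital Treatment Period list.

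For the study cohort the cost is a few derived variables, since weight and PN prescription are already recorded. The open item is the historical controls: the sponsor must confirm that weight, PN prescription and lipid amount can be recovered for them over follow-up. If weights are missing, the per-kg comparison with controls cannot be made for those patients, and infusion days per week becomes the main comparable measure. No treatment, visit or sample size changes.
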